3.3 Randomisation

Randomisation will be undertaken using an online randomiser tool

(<https://www.randomizer.org/>) to randomise eligible participants into one of the four intervention arms.

3.4 Participants

Inclusion criteria

- i. Females aged between 18 and 65 years.
- ii. Obese (BMI 30 kg/m² - 45kg/m²) with a maximum body weight of 130kg
- iii. Otherwise healthy

Exclusion criteria

- i. Recent body weight loss/gain >5% within previous 3 months
- ii. Currently taking part in an active diet program
- iii. Current medications or other conditions known to affect body weight and appetite
- iv. Previous bariatric surgery
- v. Diagnosed with impaired liver or kidney function
- vi. Significant current disease such as type 2 diabetes, cardiovascular disease, or cancer; or digestive disease including inflammatory bowel syndrome/disease (IBS/D), ulcerative colitis (UC), Crohn's disease
- vii. Systolic blood pressure \geq 160 mmHg and/or diastolic blood pressure \geq 100mmHg
- viii. Depression or any other anxiety disorder known to affect appetite
- ix. Unable to consume food items included in the study, or hypersensitivities or allergies to these foods (based on Food Preference Questionnaire)
- x. Smokers or ex-smokers who have given up smoking for less than 6 months
- xi. Pregnant or breastfeeding women
- xii. Unwilling/unable to comply with the study protocol

3.5 Power calculation

The power calculation formula for detecting the difference between two means is used:

$$k = \frac{n_2}{n_1} = 1$$
$$n_1 = \frac{(\sigma_1^2 + \sigma_2^2/K)(z_{1-\alpha/2} + z_{1-\beta})^2}{\Delta^2}$$
$$n_1 = \frac{(4^2 + 4^2/1)(1.96 + 0.84)^2}{2.82^2}$$
$$n_1 = 32$$
$$n_2 = K * n_1 = 32$$

n_1, n_2 = Sample size for group 1 and group 2

K = Ratio of sample size for group 2 to group 1

σ = Standard deviation using previous data

$Z_{1-\alpha/2}$: This depends on level of significance, for 5% this is 1.96

$Z_{1-\beta}$: This depends on power, for 80% this is 0.84

Δ = Clinically significant difference between two groups

It is performed based on the data from a similar study conducted in The Netherlands (Soenen et al., 2012). The HP diet in this study resulted in a mean body weight reduction of 14kg over 12 weeks, with a standard deviation of 4kg. By applying the data into the formula, it showed that a sample size of 32 participants per diet arm is required to detect a difference of 2.8kg (20% of 14kg) in body weight between two diet groups (HP vs LC) with 80% power and a 5% level of significance. Assuming a dropout rate of 10%, we target recruitment of 35 participants per diet arm. Since there are 4 intervention diets (HPNC, HPLC, NPNC, and NPLC) in this study, a total of 140 participants will be recruited.

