2.3 Hypothesis

A higher-protein LED diet may induce greater body weight loss than a normal-protein LED diet, irrespective of CHO content, during a period of rapid weight loss. In addition, a higher-protein LED may suppress hunger and promote fat loss while retaining greater fat-free mass.

3. Methods

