3.1 Trial Design

This trial is conducted as a 4-arm parallel intervention study, comparing 4 different weight loss LEDs based on a 2 x 2 factorial design. The study will comprise 2 higher-protein diet treatments and 2 lower-CHO diet treatments.

Table 1. Four treatments in the study.

Components	High-Protein (HP)	Normal-Protein (NP)
Normal-CHO (NC)	HPNC	NPNC
Low-CHO (LC)	HPLC	NPLC

Each eligible participant will be randomised to one of the 4 intervention arms and will need to adhere to the assigned diets for 8 weeks. The target daily energy intake during the 8-week weight-loss period is approximately 40% of their daily energy requirement at the time of screening, calculated using the Harris-Benedict's Equation and participants will be assigned to the nearest 3.9 or 4.6MJ diet plan. An LED will be used in part to achieve this dietary target.

HP diet (50en%) is aimed to provide 1.2g/kg/day protein; whereas NP diet (35en%) is aimed to provide 0.8g/kg/day protein. Conversely, the LC arm is aimed to provide 28en% CHO; whereas the NC arm is aimed to provide 40en% CHO. The balance of energy for each diet treatment will comprise dietary lipid. The macronutrient composition of each diet during the weight-loss period is shown in Table 2; whereas the absolute intake of macronutrients (grams) for each intervention is shown in Appendix 1. Throughout the intervention period, participants are asked to maintain their usual physical activity level.

Table 2. Macronutrient composition of the intervention diets.

High-Protein (HP)		Normal-Protein (NP)	
Normal-CHO (NC)	Low- CHO (LC)	Normal- CHO (NC)	Low- CHO (LC)
50en% Protein	50en% Protein	35en% Protein	35en% Protein
40en% CHO	28en% CHO	40en% CHO	28en% CHO
10en% Fat	22en% Fat	25en% Fat	38en% Fat

en%, percentage of energy

Investigators will explain the macronutrient composition of the diet to participants either individually or as a group of participants who are assigned to the same intervention arm.

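### The power calculation names HP vs LC, but the aim, objectives and hypothesis set HP vs NP: the primary comparison must be reconciled and its power restated

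*Protocol*

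**What the plan says.** Protocol Section 3.1 crosses protein (HP, NP) with carbohydrate (NC, LC), giving four arms: HPNC, HPLC, NPNC and NPLC. Body weight change is the primary outcome (Section 3.11).

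Two descriptions of the comparison run through the protocol.

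- **HP vs NP.** The hypothesis in Section 2.3 reads: "A higher-protein LED diet may induce greater body weight loss than a normal-protein LED diet, irrespective of CHO content". Section 2.2 sets the two high-protein diets against the two normal-protein diets. Section 2.1 aims at a protein effect that does not depend on low CHO.
- **HP vs LC.** Section 3.5 chooses the sample size "to detect a difference of 2.8kg (20% of 14kg) in body weight between two diet groups (HP vs LC) with 80% power". The introductory summary (before Section 1), the last paragraph of Section 1.5 (when it speaks of power) and the preload breakfast text in Section 3.8 also set higher protein against lower CHO.

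The protocol states no power for HP vs NP.

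**The concern.** HP and LC are not two groups in this design. They are levels of different factors, and HPLC belongs to both. A contrast between them is neither a main effect nor the interaction, and it changes protein and CHO together. Separating those two is the purpose of the trial.

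An analysis plan written from this protocol could defend either HP vs NP or HP vs LC as primary, and the two can lead to opposite conclusions. If higher protein and lower CHO help equally, HP vs LC is zero although the hypothesis is true. The power figure that readers will rely on is also attached to the wrong label, so the detectable difference for the hypothesis is unstated.

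**Working it through.** **Inputs, all from Section 3.5:** two-sided 5% (z = 1.96); 80% power (z = 0.84); SD 4 kg in each group; difference 2.8 kg (2.82 in the printed formula); equal groups; 32 completers per arm, hence 4 x 32 = 128. The SD and the 14 kg base come from a cited study with a "mean body weight reduction of 14kg over 12 weeks, with a standard deviation of 4kg".

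**1. The protocol's own figure.** n = 2 x SD² x (1.96 + 0.84)² / difference².
- Difference 2.8: 2 x 16 x 7.84 / 7.84 = 32.0.
- Difference 2.82: 2 x 16 x 7.84 / 7.95 = 31.5, rounded up to 32.

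The stated 32 per arm is reproduced. Power at 32 vs 32 for 2.8 kg is 80.0% by the normal approximation and 78.7% by the t distribution.

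**2. What HP vs LC estimates.** Let P be the extra weight loss from HP over NP and L the extra loss from LC over NC. Assume the effects add. With NPNC = m, we have HPNC = m + P, NPLC = m + L and HPLC = m + P + L.
- Single arms: HPNC and NPLC are the only pair in which one arm is HP but not LC and the other is LC but not HP. Their difference is P - L.
- Pooled margins: (HPNC + HPLC)/2 - (HPLC + NPLC)/2 = (HPNC - NPLC)/2 = (P - L)/2. The shared arm cancels.
- HP vs NP: (HPNC + HPLC)/2 - (NPNC + NPLC)/2 = P.

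When P = L, both HP vs LC readings are zero whatever the size of P. As an illustration with assumed effects, take P = 2.8 kg and L = 1.4 kg. HPNC vs NPLC then has a true difference of 1.4 kg and a standard error (SE) of 4 x sqrt(2/32) = 1.00 kg. Its power is Φ(1.40 - 1.96) = about 29%.

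**3. Power for the contrasts of the factorial at 32 completers per arm.**

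| Contrast | SE (kg) | Power at 2.8 kg | 80% power at |
|---|---|---|---|
| HP vs NP main effect, 64 vs 64 | 4 x sqrt(2/64) = 0.71 | Φ(3.96 - 1.96) = 97.7% (t-based 97.6%) | 2.80 x 0.707 = 1.98 kg |
| HP vs NP within one CHO level, 32 vs 32 | 4 x sqrt(2/32) = 1.00 | Φ(2.80 - 1.96) = 80.0% | about 2.8 kg |
| Protein-by-CHO interaction | 4 x sqrt(4/32) = 1.41 | Φ(1.98 - 1.96) = 50.8% | 2.80 x 1.414 = 3.96 kg |

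The difference stated in Section 3.5 is 2.8/1.98 = 1.41 times the one that the HP vs NP main effect can detect with the same power.

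**The case against.** The strongest reply is that this is a label with no effect on enrolment. The formula uses only the difference, SD, significance level and power. Nothing in it is specific to HP vs LC, so 32 per arm gives about 80% for any two single arms that differ by 2.8 kg, including HPNC vs NPNC and HPLC vs NPLC. That stands.

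Several stronger readings are tempting, and the documents do not support them.

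- A reader might infer that the trial is too small for its hypothesis. The reverse holds on the protocol's inputs: the HP vs NP main effect is better powered than the stated 80%.
- A reader might infer that the trial never asks about HP vs LC. The introductory summary and Sections 1.5 and 3.8 do describe it that way. The defect is two competing descriptions.
- A reader might infer that the sentence in Section 3.1, "The study will comprise 2 higher-protein diet treatments and 2 lower-CHO diet treatments", is wrong. It is literally true, since HPLC counts in both pairs, and Table 1 directly below it shows the crossing.
- A reader might infer a multiplicity problem from comparing all pairs of arms. The protocol plans no such set of tests, and multiplicity may be handled in an analysis plan that was not available.

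It is also fair to say that no passage prescribes a test of HP minus LC, so the illustration in the check shows what could happen, not what is planned. This does not remove the point. Section 3.5 states a specific contrast that conflicts with Sections 2.1 to 2.3. That is a contradiction in the text, not a detail left to the analysis plan.

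**Conclusion.** The concern holds as an internal contradiction about the primary comparison. The power statement names a contrast that cannot isolate the protein effect, and the power of the hypothesised contrast is not given. At the planned size, that contrast has about 98% power at 2.8 kg and 80% at about 2.0 kg. Enrolment need not change on this account.

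The part of the hypothesis that claims the effect regardless of CHO level is weaker. A 2.8 kg interaction would be detected only about half the time, so a non-significant interaction test would say little.

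These figures assume SD 4 kg, 32 completers in every arm and the normal approximation. The reading of HP vs LC as P - L, or half of it, assumes additive effects. The inputs come from a 12-week study, while this trial lasts 8 weeks. If the 2.8 kg shrank in proportion to time (an assumption: 2.8 x 8/12 = 1.87 kg) with SD unchanged, power would be about 75% for the main effect and 46% for two single arms. That is a separate matter from the choice of contrast.

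**What to change.** - In Section 3.5, replace the HP vs LC label with the protein main effect, HP (HPNC + HPLC) vs NP (NPNC + NPLC), as the single primary contrast at two-sided 5%.
- In the same section, restate its power and detectable difference at the unchanged sample size: about 98% at 2.8 kg, and 80% at about 2.0 kg, with 64 vs 64 completers and SD 4 kg.
- Align the introductory summary, Section 1.5 and the preload text in Section 3.8 with Sections 2.2 and 2.3.
- Support the claim that the effect holds at either CHO level with HP minus NP estimates and 95% confidence intervals within NC and within LC. Each interval would be about ±1.96 x 1.00 = ±2.0 kg. Do not rest the claim on a non-significant interaction.

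The cost is protocol wording only, with no extra participants. It should be done before outcome data are seen by arm. The small downside is that the main effect averages over the two CHO levels and comparisons of single arms become secondary.

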3.6 Participant recruitment and pre-screening

Recruitment of participants will be conducted in the Auckland region using convenient sampling method. Participants will be recruited through various media, by posting the ethics-approved advertisement on newspapers, press release, email, social gatherings, public notice boards, blog sites and medical centres. Participants who completed previous studies at HNU will be invited back for this study if they wish to participate.

Individuals who are interested in this study may contact the investigators for a remote pre-screening (either online questionnaire or telephone interview) and a Participant Information

Sheet (PIS), which will be emailed or posted to them. Data on age, ethnicity, reported body weight and height, brief medical record, current medications will be collected during the pre-screening to ensure that inclusion/exclusion criteria are met before attending Human Nutrition Unit (HNU) for a screening visit.

3.7 Clinic visits

The summary of the screening and clinical investigation days (CIDs) are shown in Table 5. Participants are required to attend all visits.

Table 5. Agenda during each visit at HNU.

Agenda	Screening	Baseline	8-week weight loss	
		CID 1 Week 0	CID 2 Week 4	CID 3 Week 8
Informed consent	✓			
Anthropometric measurement ¹	✓	✓	✓	✓
Blood pressure	✓	✓	✓	✓
Fasting blood sample	✓	✓	✓	✓
24-hour urine		✓	✓	✓
4-day food record		✓	✓	✓
DXA		✓		✓
Preload challenge		✓		✓
3-factor eating questionnaire		✓		✓
Baecke Questionnaire		✓		✓
Dietary consultation		✓	✓	✓

¹ Anthropometric measurements include body weight, body height and waist/hip circumference.

Screening visit

During the screening visit, participants are required to arrive at HNU after an overnight fast of at least 10 hours, having consumed nothing but water since the prior evening meal.

Participants will receive a Participant Information Sheet (PIS) and the study will be explained by a researcher. Participants will be given the opportunity to ask questions and written informed consent will be obtained. Participants will then be screened for eligibility. Demographics (age and ethnicity) and anthropometry (height, body weight, waist and hip circumference, BMI and blood pressure) will be recorded. A venous blood sample will be collected to check for fasting plasma glucose (FPG) concentration on site to screen for diabetes. When FPG is ≥ 7.0 mmol/L, another venous blood sample will be collected to check for HbA1c. When HbA1c ≥ 50 mmol/L, participant's GP will be contacted to confirm whether the participant has diabetes.

After confirming the participant's eligibility, participants will be given a urine bottle, alongside verbal and written instruction on how to collect urine samples. Additionally, participants will be taught to complete a 4-day food record (3 weekdays and 1 weekend) by investigators. Participants are asked to collect the urine sample on one of the days of the food record. The urine samples and 4-day food records will be completed during the week before attending CID1 and CID 3.

Clinical Investigation Days (CIDs)

For all CIDs, participants are required to arrive at HNU after an overnight fast of approximately 10 hours, having consumed nothing but water since the prior evening meal.

At CID1 (Week 0), the visit will take approximately 5 hours. Participants are required to arrive at HNU at 8am for a preload challenge (see Section 3.7). After the preload challenge, participants will be given a lunch meal. Participants are also required to complete a 3-factor eating questionnaire (3FEQ) and a Baecke Questionnaire. It will be followed by a dietary consultation session with an investigator. Finally, participants will be invited to the Auckland City Hospital to perform a body composition scan using DXA (see Section 3.9). The 8-week weight loss intervention period will be commenced after CID1, whereby participants are required to adhere to their assigned intervention diets (HPNC/HPLC/NPNC/NPLC). The intervention comes to the end upon the completion of CID3.

At CID 2 (Week 4), the visit will take approximately 30 minutes. Participants are required to arrive in the morning at any time between 8:00am and 11:00am for their anthropometric measurements to be taken, following by blood pressure. Then a Research Nurse will collect 7mL of fasting blood. Finally, there will be a dietary consultation session with an investigator.

At CID 3 (Week 8), the visit itinerary will be the same as CID 1. The study is completed upon the end of CID 3 visit.

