3.8 Preload challenge

The protocol for preload challenge is adapted from the standard international guidelines as recommended by Blundell et al. (2010). The purpose of this preload challenge is to investigate the change in appetite associated with each of the 4 weight-loss intervention diets.

Schedule for the preload challenge visit

The preload challenge will take place at the Appetite Research Centre in HNU. Participants will arrive at HNU at 8:00am after an overnight fast of approximately 10 hours, having consumed nothing but water since the prior evening meal. Upon arrival, the participant will be given a glass of water (250mL) to drink and their anthropometric measurements will be taken, followed by blood pressure.

For all participants, baseline Visual Analogue Scale (VAS) ratings of appetite will be measured at 8:50am (t = 0 min), before the breakfast. At the same time, a 10mL fasting blood sample will also be collected (t = 0 min). At 9:00am participants will be given a preload breakfast and allowed 15 minutes to consume all components of the meal. The meal will be given within an individual dining booth. Participants will rate the palatability of the preload breakfast using standard VAS methods. At specific time points over a period of 3.5 hours (t = 0, 15, 30, 60, 90, 120, 150, 180 and 210 mins), participants will rate appetite-related sensations (hunger, fullness, satisfaction, thoughts of food, thirsty and nausea) using standard VAS methods. At 11:05am, participants will be given a glass of water (250mL) to drink for rehydration. Participants should finish the glass of water within 10 minutes.

A subset of participants who consent for repeat blood sampling will undergo forearm venous cannulation by the Research Nurse. Apart from fasting blood sample being collected (t = 0 min; 10mL blood), blood samples will also be collected intermittently after preload breakfast (t = 15, 30, 60, 90, 120, 150, 180, 210 mins; 7mL blood at each time point). Collectively, a total of 66mL of blood will be collected from these participants on each of the 2 preload study days. The participants will complete the preload challenge study at 12:30pm, and the cannula will be removed.

The summary of the visit schedule for the preload challenge is as follows:

08:15am – 250mL water to drink
08:30am – cannulation
08:50am – VAS, baseline blood sample (t0)
09:00am – preload breakfast
09:15am – VAS, blood sample (t15)
09:30am – VAS, blood sample (t30)

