10:00am – VAS, blood sample (t60)
10:30am – VAS, blood sample (t90)
11:00am – VAS, blood sample (t120)
11:05am – 250mL water to drink
11:30am – VAS, blood sample (t150)
12:00pm – VAS, blood sample (t180)
12:30pm – VAS, blood sample (t210)

Preload breakfast

The Cambridge LED meal replacement along with peanut butter toast and egg will be used as the preload breakfast. A glass of 250mL water will also be given to drink for hydration and aid swallowing. The identical preload will be used at Week 0 and Week 8, irrespective of the diet intervention arm. For example the preload may be a 227mL meal replacement shake, which contains approximately 1.8MJ, 29g protein, 39.2g CHO and 16.8g fat. The purpose of using identical preload for all participants at all preload challenge occasions is so that participants will be exposed to the same acute stimuli (i.e. the preload breakfast), and any difference in the appetite response can be expected to be linked to the differences in long-term stimuli (i.e. high-protein vs low-CHO diets).

Visual analogue scales (VAS)

Appetite-related VAS will be used following the international methodology of Blundell et al. (2010). The following questions will be used: “How hungry do you feel? / How full do you feel? / How satisfied do you feel? / How much do you think you can eat now / How nauseous do you feel?” anchored on the left by “I am not hungry at all / I am not full at all / I am completely empty / nothing at all / not nauseous at all” and “I am as hungry as I have ever been / I am totally full / I cannot eat another bite / a large amount / very nauseous” on the right. Participants will mark their responses by placing a vertical line across the 100-mm scale according to their subjective feelings (Fig 1).

Hunger

- How hungry do you feel?
- ANCHOR: 'I am not hungry at all' vs. 'I am as hungry as I have ever been'

Fullness

- How full do you feel?
- ANCHOR: 'I am not full at all' vs. 'I am totally full'

Satisfaction

- How satisfied do you feel?
- ANCHOR: 'I am completely empty' vs. 'I cannot eat another bite'

Thoughts of food

- How much do you think you can eat now
- ANCHOR: 'nothing at all' vs. 'a large amount'

Thirst

- How thirsty do you feel?
- ANCHOR: 'I am not thirsty at all' vs. 'I am as thirsty as I have ever been'

Nausea

- How nauseated do you feel?
- ANCHOR: 'I do not feel nauseated at all' vs. 'I am as nauseated as I have ever been'

[figure not shown]

Figure 1. Example of VAS.

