3.10 Dual Energy X-Ray Absorptiometry (DXA)

DXA body composition measurement will take place at Department of Surgery Body Composition Unit at Auckland City Hospital. DXA is based on the 3 component model of body composition, and uses 2 x-ray energies to measure body fat mass, lean mass, and bone mineral density. A rapid scan iDXA (GE-Lunar, Madison, WI) designed to allow scanning of larger individuals with high body weight and BMI will be used. The participant is required to lie recumbent on the open scanner bed for approximately 10 minutes. Body composition comprising total body fat, fat-free soft tissue and bone mineral content as well as regional fat deposition will be determined from DXA whole-body and segmental scans. DXA scans are a low-risk research tool, commonly used in nutrition intervention trials. A single scan provides exposure similar to that of a 1 hour flight between Auckland and Wellington.

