3.11 Outcome variables

Primary outcome

- i. Change in body weight.

Secondary outcome

- i. Plasma concentration of appetite-related biomarkers.
- ii. VAS ratings for appetite sensations following a preload breakfast challenge.
- iii. Change in body composition (fat mass and fat-free mass).

Other

- i. Other metabolic parameters and urinary nitrogen.
- ii. 4-day food records.

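### The DXA scan follows a lunch of unstated size at an unfixed interval, which adds avoidable noise to the change in fat-free mass

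*Protocol*

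**What the plan says.** Section 3.7 (Clinic visits) describes CID1 in order. Participants arrive fasted for the preload challenge. Then: "After the preload challenge, participants will be given a lunch meal". The questionnaires and a dietary consultation come next, and the scan is last: "Finally, participants will be invited to the Auckland City Hospital to perform a body composition scan using DXA". Week 8 follows the same plan: "At CID 3 (Week 8), the visit itinerary will be the same as CID 1".

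Section 3.8 schedules three glasses of water before that lunch:
- on arrival: "Upon arrival, the participant will be given a glass of water (250mL) to drink"
- with the breakfast: "A glass of 250mL water will also be given to drink for hydration and aid swallowing"
- late morning: "At 11:05am, participants will be given a glass of water (250mL) to drink for rehydration"

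The same section makes the preload breakfast identical in all arms and at both weeks. No such statement is made for the lunch.

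Section 3.10 describes what the scan yields: "Body composition comprising total body fat, fat-free soft tissue and bone mineral content". It sets no condition on fasting, voiding or time since eating. Change in fat mass and fat-free mass is secondary outcome iii in Section 3.11. Retention of fat-free mass is also objective iii in Section 2.2 and part of the hypothesis in Section 2.3.

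**The concern.** The scan divides the body into fat, fat-free soft tissue and bone mineral. Recently eaten food and retained water are not bone and are mostly not fat, so they are counted mainly as fat-free soft tissue. The outcome is a difference between two scans. Whatever differs between a participant's two visits in lunch mass, bladder content or time since lunch therefore goes into her measured change as error.

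Participants arrive fasted, and the protocol takes care to standardise the breakfast. It then places an unstandardised meal between the fasted state and the scan. At stake is some precision on a secondary outcome that carries part of the trial's hypothesis.

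**Working it through.** **The plan's own figure.** The only sample-size calculation (Section 3.5) is for body weight: (4² + 4²) × (1.96 + 0.84)² / 2.82² = 31.5, rounded up to 32 per arm. It reproduces, but it does not concern fat-free mass. The protocol gives no SD for change in fat-free mass and no lunch weight.

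**What is constant and what is not.**
- Water: 3 × 250 mL = 750 mL, scheduled for every participant at both preload visits. It largely cancels from the change and from arm contrasts.
- Preload: identical across arms and visits. It also largely cancels.
- Lunch: no weight, composition or rule on how much is eaten.
- Interval to the scan: not fixed. The visit is put at about 5 hours from 8am, so it ends near 1pm. The preload challenge ends at 12:30pm. Lunch, two questionnaires, a consultation and the journey to the hospital follow.
- Voiding before the scan: not stated.

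**Loss of precision.** All inputs here are assumptions:
- S, the SD of fat-free-mass change without lunch error: 1.5 kg (range 1 to 2)
- e, the between-person SD of lunch mass per scan: 0.2 to 0.4 kg
- r, the correlation of a person's lunch mass between the two visits: 0 or 0.5

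Added variance of the change = 2e²(1 − r). Fraction of effective sample size lost = 2e²(1 − r) / [S² + 2e²(1 − r)].

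| S (kg) | e (kg) | r | Calculation | Loss |
|---|---|---|---|---|
| 1.5 | 0.2 | 0 | 0.08 / 2.33 | 3.4% |
| 1.5 | 0.4 | 0 | 0.32 / 2.57 | 12.5% |
| 1.5 | 0.2 | 0.5 | 0.04 / 2.29 | 1.7% |
| 1.5 | 0.4 | 0.5 | 0.16 / 2.41 | 6.6% |
| 2 | 0.2 | 0 | 0.08 / 4.08 | 2.0% |
| 1 | 0.4 | 0 | 0.32 / 1.32 | 24.2% |

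If lunch is the same for everyone, e is near zero and so is the loss. At S = 1.5 kg and r = 0, 32 participants in an arm carry the information of about 31 (32 × 0.966) to 28 (32 × 0.875).

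In kilograms, the difference detectable with 80% power at 32 per arm is 2.80 × SD × √(2/32):
- without lunch error: 2.80 × 1.5 × 0.25 = 1.05 kg
- with e = 0.2: 2.80 × √2.33 × 0.25 = 1.07 kg
- with e = 0.4: 2.80 × √2.57 × 0.25 = 1.12 kg

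**Conditional bias.** Suppose lunch were eaten to appetite and the high-protein arms, being less hungry, ate 0.2 kg less at Week 8 (an assumption). Their apparent fat-free mass would fall by at most 0.2 kg relative to the others, and by less to the extent that the meal contains fat. That is at most 0.2 / 1.05 = 19% of the detectable difference at 32 per arm. The sign is against the hypothesised benefit.

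**The case against.** Four arguments carry weight.

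**Water.** A reader might infer that 750 mL of water before the scan distorts the outcome. The documents do not support this. The volume and timing are the same for all arms and both visits, and part of the water will have been absorbed or voided by the time of the scan.

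**Bias between arms.** A reader might also infer that the trial's own appetite hypothesis makes lunch intake, and so fat-free mass, differ by arm. That needs a lunch eaten freely, a real difference in hunger at Week 8 and a resulting difference in mass eaten. The protocol establishes none of these. It calls the variable home meal ad lib but says only that the visit lunch is given, and lunch intake is not an outcome. Any such bias would hide a high-protein benefit, not create one. Nor would it pass through in full, since fat in the meal would not be read as fat-free tissue.

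**Lunch may in practice be fixed.** Table 3 in Section 3.2 makes lunch on the diet a fixed meal replacement, to be finished, and the intervention runs until CID3 is completed. This is a fair point for Week 8, but it does not settle the matter. The text does not say that the visit lunch follows Table 3. The diet starts only after CID1, so Table 3 cannot govern the baseline lunch.

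**Operational detail.** Lunch weight and scan preparation often sit in operating procedures, so their absence alone would be a weak point. The order of lunch and scan, however, is stated in the protocol, and it is the order that creates the error.

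The first two arguments stand and confine the concern to noise. The third stands as a possibility that would bring the loss close to zero.

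**Conclusion.** The concern holds as a minor design point. The stated order puts an unspecified lunch and an unfixed interval before the scan at both visits. This adds avoidable error to the change in fat-free mass.

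The size rests wholly on assumed values. With an SD of change of 1.5 kg and a lunch-mass SD of 0.2 to 0.4 kg, the loss is about 3% to 12% of effective sample size with uncorrelated lunches and about 2% to 7% at a correlation of 0.5. It is near zero if lunch is in practice standardised. With uncorrelated lunches and an SD of change anywhere from 1 to 2 kg, the range is 2% to 24%.

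The documents do not support a claim that the arm comparison is biased. If lunch is eaten to appetite and hunger differs by arm at Week 8, the result would understate retention of fat-free mass in the high-protein arms. Body weight is measured on arrival, before breakfast and lunch, so the primary outcome is not affected.

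**What to change.** In Section 3.7, move the lunch to after the DXA scan at CID1 and CID3, for example as a packed meal. The breakfast and water would still precede the scan, but they are standardised. A line in Section 3.10 asking for voiding before the scan would deal with most of what is left.

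If the order cannot change, serve a lunch and drink of fixed weight, identical in all arms and at both visits, with voiding and a set interval before the scan.

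The cost is a somewhat later lunch under the first option, or weighing the lunch and keeping to a timetable under the second. Neither touches the diets, the sample size or the primary outcome.
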